The trial will be conducted in accordance with International Council on Harmonization Good Clinical Practice (ICH GCP), and applicable United States (US) Code of Federal Regulations (CFR). The Principal Investigator/Sponsor-Investigator will assure that no deviation from, or changes to the protocol will take place without prior agreement from the funding agency and documented approval from the Institutional Review Board (IRB), and the Food and Drug Administration (FDA), if applicable, except where necessary to eliminate an immediate hazard(s) to the trial participants. All personnel involved in the conduct of this study have completed Human Subjects Protection and ICH GCP Training.

The protocol, informed consent form(s), recruitment materials, and all participant materials will be submitted to the IRB for review and approval. Approval of both the protocol and the consent form(s) must be obtained before any participant is consented. Any amendment to the protocol will require review and approval by the IRB before the changes are implemented to the study. In addition, all amendments to the protocol will be submitted to FDA prior to implementation. All changes to the consent form(s) will be IRB approved; a determination will be made regarding whether a new consent needs to be obtained from actively enrolled participants, using a previously approved consent form.

1 PROTOCOL SUMMARY

1.1 SYNOPSIS

Title: A Randomized, Double-Blinded Single Site Study to Evaluate the Efficacy of Erenumab for Treatment of Idiosyncratic Facial Pain Mimicking Rhinosinusitis

Study Description:

Objectives: Primary Objective: To compare change from baseline in mean number of days per month with significant pain or pressure between treatment and placebo groups at 4 to 6 months.

Secondary Objectives:

1. To compare change from baseline in mean number of days per month with significant pain or pressure between treatment and placebo groups at 1 month and 3 months.

2. To compare mean number of days per month with significant pain or pressure comparing baseline to 1, 3, and 4 to 6 months within each group (intragroup analysis)
3. To compare change from baseline between treatment and placebo groups at 1, 3, and 4 to 6 months for the following:

- a. Sinonasal Outcome Test-22 (SNOT-22)
- b. Migraine Functional Impact Questionnaire (MFIQ)
- c. Mean number of days per month with significant nasal congestion and rhinorrhea.
- d. Doses of rescue pain medications taken
- e. Mean daily pain score

Study Population: Patients presenting with at least three months of chronic or episodic midfacial pain or pressure referred for evaluation of sinusitis and found to have no endoscopic or radiographic evidence of sinusitis

[figure not shown]
Phase: IV

Description of Sites/Facilities Enrolling Participants: Duke University Health System

Description of Study Intervention: Erenumab vs. Placebo

Study Duration: 34 months
Participant Duration: 7 months

1.2 SCHEMA

1.3 SCHEDULE OF EVENTS (SOE)

Procedures	Screening / Lead-in Period	Baseline / Randomization & Initial Treatment Visit	Treatment Visit	Treatment Visit	Treatment Visit	Treatment Visit	Treatment Visit	Follow-up / End of Study visit	Unscheduled Visit
	Visit 1	Visit 2	Visit 3	Visit 4	Visit 5	Visit 6	Visit 7	Visit 8	Unscheduled
	Day -30 to -1	Day 0 (+6 days)	Day 30 (+/- 6 days)	Day 60 (+/- 6 days)	Day 90 (+/- 6 days)	Day 120 (+/- 6 days)	Day 150 (+/- 6 days)	Day 180 (+/- 6 days)	N/A
Informed Consent	x								
Demographics	x								
Medical History	x								
Randomization		x							
Study drug Administration		x	x	x	x	x	x		
Concomitant medication review	x	x	x	x	x	x	x	x	x
Physical exam	x	x	x	x	x	x	x	x	x
Home BP Monitoring (BP checks daily x 7 days following first dose of drug administration, then weekly and when symptomatic throughout duration of study)									→
Sinus CT Scan ¹	x								
Pregnancy test ²	x	x	x	x	x	x	x		
Endoscopy ³	x								
Review subject pain and blood pressure diary compliance and instruct subject on daily use	x	x	x	x	x	x	x	x	x
Migraine Assessment Tool (MAT)	x								

Procedures	Screening / Lead-in Period	Baseline / Randomization & Initial Treatment Visit	Treatment Visit	Treatment Visit	Treatment Visit	Treatment Visit	Treatment Visit	Follow-up / End of Study visit	Unscheduled Visit
	Visit 1	Visit 2	Visit 3	Visit 4	Visit 5	Visit 6	Visit 7	Visit 8	Unscheduled
	Day -30 to -1	Day 0 (+6 days)	Day 30 (+/- 6 days)	Day 60 (+/- 6 days)	Day 90 (+/- 6 days)	Day 120 (+/- 6 days)	Day 150 (+/- 6 days)	Day 180 (+/- 6 days)	N/A
Sinonasal Outcome Test questionnaire (SNOT-22)	x				x			x	
Migraine Functional Impact questionnaire (MFIQ)	x				x			x	
Pain Location Diagram	x								
Adverse event review and evaluation	x	x	x	x	x	x	x	x	x
Subject Compensation (clincard)	x	x	x	x	x	x	x	x	

1 - Most recent Sinus CT scan obtained as SOC should be within 12 months of the screening visit. If > 12 months then repeat for study purposes if not clinically indicated.

2 - Serum pregnancy test at screening, then urine pregnancy test on subsequent visits

3 - Endoscopy at screening as standard of care (SOC). If not done as SOC within 3 months of the screening visit, then complete it as a research procedure and charged to the study. Repeat only as clinically indicated.

1.4 OBJECTIVES AND ENDPOINTS

OBJECTIVES	ENDPOINTS
Primary:	
To compare change from baseline in mean number of days per month with significant pain or pressure between treatment and placebo groups at 4-6 months.	Change in mean number of days per month with significant midfacial pain or pressure (defined as greater than 4/10) from baseline to 4-6 months
Secondary:	
To compare change from baseline in mean number of days per month with significant pain or pressure between treatment and placebo groups at 1 month and 3 months.	Change in mean number of days per month with significant midfacial pain or pressure (defined as greater than 4/10) from baseline to 1 month and 3 months.
To evaluate the efficacy of erenumab in reducing mean number of days with facial pain (intragroup change)	Change in mean number of days per month with significant pain or pressure comparing baseline to 1, 3, and 4-6 months within each group.
To evaluate the efficacy of erenumab in reducing burden of rhinosinusitis symptoms	Change in 22-Item Sinonasal Outcomes Test (SNOT-22) questionnaire score from baseline to 1, 3, and 6 months
To evaluate the efficacy of erenumab in improving functional impact of migraine-related facial pain	Change in each of the five domains of the Migraine Functional Impact Questionnaire (MFIQ) from baseline to 1, 3, and 6 months
To evaluate the efficacy of erenumab in improving associated symptoms of nasal congestion and rhinorrhea	Change in average number of days per month with significant nasal congestion or rhinorrhea (defined as greater than 4/10) from baseline to 1, 3, and 4-6 months
To evaluate the efficacy of erenumab in reducing pain medication usage	Change in doses of rescue pain medications taken from baseline to 1, 3, and 4-6 months
To evaluate the efficacy of erenumab in reducing daily pain severity	Change from baseline in mean daily pain score from baseline to 1, 3, and 4-6 months

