During the screening visit, eligible subjects will receive instructions and training on use of the ecological momentary assessment (EMA) via mobile phone. If for any reason they cannot complete the EMA via a mobile phone, a paper copy will be available to the participant. During the 30-day lead-in period, subjects will be expected to score on a scale of 1 to 10 their symptoms of pain/pressure, nasal congestion, and rhinorrhea as well as any rescue medicines taken for pain each day. Subjects will be instructed to return to the site at the end of the 30-day lead-in period for Visit 2. During the 30-day lead-in period, subjects must record a minimum of 20 (67%) daily diary entries to be eligible for randomization during visit 2. This will be evaluated through the review of the EMA daily data log. The coordinator may call subjects to remind them to complete the log during this time period. Subjects who do not have a minimum of 20 daily entries will be considered a screen failure and removed from the study.

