4.3 SCREEN FAILURES

Screening will occur at the baseline visit. Up to twenty screen failures are anticipated. The reason for screen failure will be documented.

Screen Failures are defined as:

- a) Patients who are not compliant with EMA or daily diary for more than 33% of triggered queries during the 30-day lead-in period.
- b) Patients who do not report at least 10 days of significant pain or pressure during the 30-day lead-in period.
- c) Patients needing prophylactic migraine medicine (meds listed under exclusion # 6) during the 30 day lead-in period.

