8.1 STATISTICAL HYPOTHESES

- Primary Efficacy Endpoint(s):
 - ε To compare change from baseline in mean number of days per month with significant pain or pressure between treatment and placebo groups at 4 to 6 months.

Null Hypothesis: In subjects with idiosyncratic facial pain mimicking rhinosinusitis, the erenumab treatment group is the same as placebo, in terms of the reduction from baseline in mean monthly days with significant pain at months 4 to 6.

Alternative Hypothesis: In subjects with idiosyncratic facial pain mimicking rhinosinusitis, the erenumab treatment group is different than placebo, in terms of the reduction from baseline in mean monthly days with significant midfacial pain at months 4 to 6.

- Secondary Efficacy Endpoint(s):

- ⊖ To compare change from baseline in mean number of days per month with significant pain or pressure between treatment and placebo groups at 1 month and 3 months.
- To compare change in mean number of days per month with significant facial pain between baseline and 1, 3, and 4-6 months within each group
- To compare change in 22-Item Sinonasal Outcomes Test (SNOT-22) between treatment and placebo groups at 1, 3, and 6 months
- To compare change in the Migraine Functional Impact Questionnaire (MFIQ) and its five subdomains between treatment and placebo groups at 1, 3, and 6 months
- To compare change in reduction of rescue medication use between treatment and placebo groups at 1, 3, and 4-6 months
- ⊖ To compare change in the mean number of days per month with significant congestion and rhinorrhea between treatment and placebo groups at 1, 3, and 4-6 months.
- To compare reduction in mean pain score between treatment and placebo groups at 1, 3, and 4-6 months

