8.4.2 ANALYSIS OF THE PRIMARY EFFICACY ENDPOINT(S)

The change in the number of days with facial pain or pressure from baseline to completion of the six-month treatment administration period will be analyzed using a linear mixed-effects model including treatment group, baseline value, scheduled visit, and the interaction of treatment with scheduled visit. Imputation is not planned. If applicable, a first-order autoregressive covariance structure is assumed. Least squares means for each treatment group, standard errors, associated 95% confidence intervals as well as the treatment difference, associated 95% confidence intervals and p-values will be reported. A two-sided significance level of 0.05 is assumed.

Additionally, we will compare the change in the mean number of days per month with significant idiosyncratic facial pain between the treatment group versus the placebo-controlled group from baseline to intermediate time points at one and three months.

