8.4.3 ANALYSIS OF THE SECONDARY ENDPOINT(S)

- The mean number of days per month with significant pain or pressure

This will be compared between baseline and 1, 3, and 4-6 months within each group. This represents an intragroup analysis as opposed to comparing treatment and placebo groups.

- 22-Item Sinonasal Outcomes Test (SNOT-22)

The change in mean scores from baseline for the SNOT-22 survey will be compared at 1, 3, and 6 months. The SNOT-22 is the most widely-used validated sinonasal questionnaire in the otolaryngologic literature.[16] Respondents rate the severity of twenty-two symptoms from a scale of 0 (no problem) to 5 (severe as can be) over the previous two weeks, for a score ranging from 0 to 110. It is self-administered and includes symptoms pertaining to multiple domains, including nasal, extranasal, sleep, and psychological. A minimal clinically important difference has been determined to be 9.[17] Analysis of the SNOT-22 will allow the assessment of changes in specific sinonasal symptoms, such as drainage and congestion, which are thought to be associated with idiosyncratic facial pain.

- Migraine Functional Impact Questionnaire (MFIQ)

The change in mean scores from baseline for each of the five subdomains of the MFIQ will be compared at 1, 3, and 6 months. The MFIQ is a self-administered 26-item questionnaire assessing the impact of migraine on five domains over the previous seven days: physical functioning (5 items), usual activities (10 items), social functioning (5 items), emotional functioning (5 items), and overall functioning (1 item).[18,19] Each item is rated on a 5-point scale, with 5 representing the greatest impact. The scores for each domain will be calculated as the sum of the items.

- Change in number of doses of rescue medication use for facial pain

The change in number of doses of rescue medication use from baseline to 1, 3, and 4-6 months will be compared. The daily data log will enable analysis of frequency, type, and numeric dose of the following rescue medications: triptans, opiates, tramadol, acetaminophen-containing medications, butalbital, antihistamines, non-steroidal anti-inflammatory drugs, decongestants, antibiotics, and steroids. The frequency (number of doses) of rescue medication use will be compared between the two groups at baseline and 1, 3, and 4-6 months

- Mean daily pain score

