The change in mean daily pain score (scale of 0 to 10) will be compared between the treatment and control groups from baseline to 1, 3, and 4-6 months.

- Mean number of days per month with significant congestion and rhinorrhea

Significant congestion and rhinorrhea will be defined as symptom score greater than 4 out of 10. The change in mean number of days per month with significant congestion and rhinorrhea from baseline to 1, 3, and 4-6 months will be compared for treatment and control groups.

Analysis of the secondary endpoints will be performed using the same methods as the primary endpoint.

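### Section 1.4 treats within-arm change from baseline as evidence of erenumab's efficacy, but that contrast cannot separate drug effect from placebo response or regression to the mean

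*Combined protocol and SAP*

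**What the plan says.** The objectives table in Section 1.4 includes the row "To evaluate the efficacy of erenumab in reducing mean number of days with facial pain (intragroup change"). Its endpoint compares baseline with 1, 3 and 4-6 months inside each arm. Section 8.1 lists the same item under its secondary efficacy endpoints: "To compare change in mean number of days per month with significant facial pain between baseline and 1, 3, and 4-6 months within each group". Section 8.4.3 is explicit about the type of comparison: "This represents an intragroup analysis as opposed to comparing treatment and placebo groups".

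On method, Section 8.4.3 says "Analysis of the secondary endpoints will be performed using the same methods as the primary endpoint". The primary method in Section 8.4.2 gives least squares means for each arm with 95% confidence intervals, "as well as the treatment difference, associated 95% confidence intervals and p-values will be reported".

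Two further passages bear on what the baseline is. Section 3.2.1 describes the daily diary: "During the 30-day lead-in period, subjects will be expected to score on a scale of 1 to 10 their symptoms of pain/pressure". Section 4.3 counts as screen failures "Patients who do not report at least 10 days of significant pain or pressure during the 30-day lead-in period". The documents do not define baseline for the diary endpoints, but the lead-in is the only pre-dose diary, so it is in effect the baseline.

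Synopsis objective 2 covers the same comparison without the word efficacy.

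**The concern.** Several rows of Section 1.4 open with the same efficacy phrase, but Section 8.1 gives the others a comparison with placebo. This row alone ties an efficacy statement to a contrast with no comparator.

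Change within the erenumab arm is the sum of drug effect, placebo response, natural course and regression to the mean. Only the randomised contrast removes the last three. Regression is expected by design, because patients are admitted on a high value of the outcome variable in the same 30 days that supply the baseline.

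At stake is what the report may claim. Under the present wording, an erenumab-arm fall whose interval excludes zero could be presented as meeting a prespecified efficacy objective beside a null between-group result.

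**Working it through.** **Inputs from the plan.** Section 8.2 gives a treatment effect of -3.0 days, SD 3.5, 33 per group, 90% power, two-sided 0.05 and 10% dropout. Section 3.1 gives 66 randomised 1:1. Section 4.3 gives the 10-day rule and "Up to twenty screen failures are anticipated".

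**The plan's own figure.** n = 2(1.960 + 1.282)² × 3.5² / 3.0² = 28.6, so 29 per arm; 29/0.9 = 32.2, so 33. The stated size reproduces and is not in dispute.

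**Within-arm precision.** Take 3.5 as the SD of change and 33 × 0.9 = 29.7, about 30 completers per arm.

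- Standard error = 3.5/√30 = 0.639
- Half-width = t(0.975, 29 df) × SE = 2.045 × 0.639 = 1.31 days, less than half the assumed 3.0-day effect

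The chance that the interval excludes zero, given a true non-drug fall δ and no drug effect, comes from the noncentral t with 29 df and noncentrality δ/0.639:

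| Non-drug fall (days) | Noncentrality | Interval excludes zero |
|---|---|---|
| 0.5 | 0.78 | 12% |
| 1.0 | 1.56 | 33% |
| 1.3 | 2.03 | 50% |
| 1.5 | 2.35 | 62% |
| 2.0 | 3.13 | 86% |
| 2.5 | 3.91 | 97% |

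**How much regression could contribute.** The documents give no baseline mean, month-to-month correlation or placebo response, so this step rests on assumptions. Let monthly counts be normal with mean μ, SD σ and correlation ρ between any two months, and let a = (10 - μ)/σ.

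- Expected failures on the 10-day rule to randomise 66: 66p/(1 - p), with p = Φ(a)
- Expected fall from selection alone: (1 - ρ) × σ × φ(a)/(1 - Φ(a))

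Example, μ = 14, σ = 5, ρ = 0.7: a = -0.8 and p = 0.212, so failures = 66 × 0.212/0.788 = 17.7. The fall is 0.3 × 5 × 0.2897/0.7881 = 0.55 days.

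The grid takes μ from 14 to 18, σ of 5 or 6 and ρ from 0.6 to 0.8, and keeps the 21 scenarios with no more than 20 expected failures on this rule. A mean of 14 with SD 6 is dropped at 22.3. Falls from regression alone run from 0.1 to 0.8 days.

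Simulated paired t-tests (n = 30, no drug effect, 20,000 runs) for baseline against the mean of months 4-6 gave the rejection rates below, with a single month in brackets:

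| μ / σ / ρ | Fall from regression | No placebo response | 1 day | 2 days |
|---|---|---|---|---|
| 14 / 5 / 0.7 | 0.55 | 16% [12%] | 78% [60%] | 99.5% [95%] |
| 15 / 6 / 0.7 | 0.64 | 15% [12%] | 67% [49%] | 97% [87%] |
| 16 / 6 / 0.7 | 0.52 | 12% [9%] | 60% [43%] | 96% [84%] |
| 16 / 5 / 0.8 | 0.22 | 8% [7%] | 73% [55%] | 99.7% [96%] |
| 18 / 6 / 0.7 | 0.32 | 7% [6%] | 48% [33%] | 92% [77%] |

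Over all 21 scenarios, regression alone gives 6-21% (single month 5-15%) against a nominal 5%. The extremes are 14/5/0.6 and 18/5/0.8. With a 1-day placebo response the range is 44-83% (single month 31-65%). With 2 days it is 87% or more (single month 70-98%).

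**Does baseline adjustment help?** No. An arm's least squares mean change is evaluated at the average baseline, which selection has already raised. A baseline-adjusted model with 30 per arm, run at the first three rows of the table, gave within-arm intervals excluding zero in 14-19% (regression only), 67-84% (1 day) and about 97% or more (2 days). The between-group test stayed at about 5%.

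**The case against.** The strongest reply is that the plan does not set up the misreading. The same variable is compared between arms at 4-6 months (primary) and at 1 and 3 months (first secondary), so every within-arm time point already has its randomised contrast. Section 8.4.1 frames the study objective as efficacy against placebo, and Section 8.1 states formal hypotheses only for that comparison. The placebo arm's change will be reported as well. The efficacy phrase may be template wording, and the p-values in Section 8.4.2 attach most naturally to the treatment difference, so within-arm p-values are not explicitly planned.

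On size, the limit of 20 screen failures covers three causes, so the upper end of the grid is generous. If the 10-day rule took no more than 10 (itself an assumption), only 16/5, 18/5 and 18/6 remain; regression alone then gives falls of about 0.1-0.4 days and 6-10% rejection. The self-reported entry criterion of 10 days a month is not modelled. The high percentages depend on a placebo response that the documents do not supply. The grid's SD of change also varies (about 2.5 to 4.2 days for months 4-6), so only the half-width and the noncentral t rates rest on the protocol's 3.5.

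The points on size stand and are reflected in the conclusion. The points on framing limit the consequence but leave the label in place. No between-group contrast is attached to this objective, and setting two within-arm results side by side does not test their difference. An interval excluding zero carries the same information as a within-arm test, whether or not a p-value is printed.

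**Conclusion.** The concern holds. Section 1.4 and the heading in Section 8.1 attach an efficacy conclusion to a contrast that cannot support one, whatever the size of the non-drug change.

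The firmest figure is the 1.31-day half-width, which rests on reading 3.5 as the SD of change with 30 completers; a non-drug fall of about 1.3 days is then as likely as not to exclude zero. Regression to the mean alone is a modest contributor and usually not significant. Placebo response, whose size is assumed here, drives the high rates.

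The primary analysis, its error rate and the sample size are untouched. The change is worth making because it governs what may be concluded from a prespecified secondary objective.

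**What to change.** - **Section 1.4:** reword the objective neutrally, following synopsis objective 2, as a description of change from baseline within each arm.
- **Sections 8.1 and 8.4.3:** state that within-arm changes are reported descriptively for both arms, with means and 95% CIs and no within-arm significance tests.
- **Section 8.4.3:** add that these changes include placebo response and regression to the mean, and that efficacy conclusions rest only on the between-group contrasts already planned at 1, 3 and 4-6 months. This sentence allows the intervals to be kept without being read as evidence of efficacy.

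The cost is wording only. Any within-arm significance tests are given up; every estimate and interval is kept, and the sample size needs no recalculation.

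### SNOT-22 and MFIQ are to be compared between arms at 1 month, but the schedule collects neither form at Day 30

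*Combined protocol and SAP*

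**What the plan says.** Four sections plan a 1-month questionnaire result. Section 1.4 lists "Change in 22-Item Sinonasal Outcomes Test (SNOT-22) questionnaire score from baseline to 1, 3, and 6 months", with matching times for each MFIQ domain. Section 8.1 makes the between-arm intent explicit for both instruments: "To compare change in 22-Item Sinonasal Outcomes Test (SNOT-22) between treatment and placebo groups at 1, 3, and 6 months", and, for the other form, "Migraine Functional Impact Questionnaire (MFIQ) and its five subdomains between treatment and placebo groups at 1, 3, and 6 months". Section 8.4.3 says "The change in mean scores from baseline for the SNOT-22 survey will be compared at 1, 3, and 6 months" and repeats those times for the five MFIQ subdomains. The synopsis (Section 1.1) puts both instruments under between-group comparisons at 1, 3 and 4 to 6 months.

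The schedule of events (Section 1.3) differs. The rows whose labels begin "Sinonasal Outcome Test questionnaire (SNOT-22" and "Migraine Functional Impact questionnaire (MFIQ" carry marks at Visit 1 (screening), Visit 5 (Day 90) and Visit 8 (Day 180) only. Visit 3 (Day 30) is blank in both rows. Section 3.2.3 has subjects at Visits 3 to 7 complete whichever questionnaires the schedule lists, so it adds nothing at Day 30.

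On analysis, Section 8.4.3 states "Analysis of the secondary endpoints will be performed using the same methods as the primary endpoint". That method, in Section 8.4.2, is a linear mixed model with treatment, baseline, scheduled visit and treatment-by-visit interaction. The same section adds "Imputation is not planned".

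**The concern.** The plan promises an analysis at a time when it collects no data. This differs from ordinary missing data, where a mixed model can borrow from the subjects who were observed. Here every subject in both arms would lack the 1-month score by design.

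If the site follows the schedule, a pre-specified comparison has to be dropped when results are reported. If staff notice the mismatch and hand out forms informally at Day 30, the data will be off-schedule and perhaps incomplete in a way nobody planned for. The loss is permanent for each subject who passes Visit 3 without the forms.

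**Working it through.** The plan gives no figure on this point. The sample size in Section 8.2 concerns the primary endpoint and plays no part. The check sets planned times against collected times.

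**Step 1. Planned against scheduled times.**

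| Place | SNOT-22 | MFIQ |
|---|---|---|
| 1.1 Synopsis | 1, 3, 4 to 6 months | 1, 3, 4 to 6 months |
| 1.4 Objectives and Endpoints | 1, 3, 6 months | 1, 3, 6 months |
| 8.1 Statistical Hypotheses | 1, 3, 6 months | 1, 3, 6 months |
| 8.4.3 Secondary endpoints | 1, 3, 6 months | 1, 3, 6 months |
| 1.3 Schedule of Events | screening, Day 90, Day 180 | screening, Day 90, Day 180 |

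The 3- and 6-month times have matching visits. The 1-month time has none.

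**Step 2. Could a table-reading fault explain it?** This is unlikely. Both rows show the same pattern, and their cells line up with the nine visit columns. Other rows of the table are coherent: study drug is marked at Visits 2 to 7 and compensation at Visits 1 to 8.

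**Step 3. Could a visit window cover 1 month?** With windows of ±6 days:
- Visit 3: 30 ± 6 = Day 24 to 36
- Visit 5: 90 ± 6 = Day 84 to 96
- Visit 8: 180 ± 6 = Day 174 to 186

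Neither post-baseline collection window overlaps the 1-month window.

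**Step 4. Could recall reach back to Day 30?** Section 8.4.3 gives a recall of two weeks for SNOT-22 and seven days for MFIQ. From the earliest Visit 5:
- SNOT-22: 84 − 14 = Day 70, which is 70 − 36 = 34 days after the latest Visit 3
- MFIQ: 84 − 7 = Day 77, which is 77 − 36 = 41 days after the latest Visit 3

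**Step 5. Could other data stand in?** The daily diary (Section 3.2.1) records pain or pressure, congestion, rhinorrhea and rescue medicine. It contains neither questionnaire, and Section 7.1 treats the questionnaires as a separate source.

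**Step 6. Could the model supply the estimate?** With scheduled visit as a factor, the post-baseline questionnaire data have two levels, Day 90 and Day 180. There is no Day 30 level, so the treatment effect at that visit is not estimable. If visit were instead treated as continuous time, a Day 30 value would be an extrapolation outside the observed range of Day 90 to Day 180.

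**Step 7. Size.**
- Scores: 1 SNOT-22 + 5 MFIQ domains = 6
- Planned comparisons: 6 × 3 times = 18
- Without data: 6 × 1 = 6
- With data: 18 − 6 = 12

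Section 8.1 can be read as adding an MFIQ total, although Section 8.4.3 defines domain scores only. On that reading there are 7 × 3 = 21 comparisons, 7 without data and 14 with. Counted by instrument, it is 2 of 2 × 3 = 6. Every count says the same thing: one time point in three.

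**The case against.** The best case on the other side concerns weight. One intermediate time point is affected, for two secondary instruments, and the plan has no testing hierarchy in which it counts. Four text sections against one table may mean no more than two omitted marks, and the documents do not show which side is the mistake. If the site hands out the forms at Visit 3 anyway, the comparison can be made.

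Most of this stands. It limits the seriousness of the point and is the reason for stating it conditionally, on the schedule being carried out as written. It does not remove the contradiction. The schedule is the operational instruction, and the visit text refers to it rather than correcting it. If two marks were left out by accident, the result for the data is the same until they are restored.

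Two further objections also stand. The 6-of-18 count treats each MFIQ domain separately, so it should not be read as more than one time point in three. The no-imputation statement is also not essential, because no reasonable imputation could supply a visit that is unobserved in every subject.

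**Conclusion.** The inconsistency is real. If the plan is carried out as written, the 1-month SNOT-22 and MFIQ comparisons have no data: 6 of 18, or 7 of 21 if an MFIQ total is intended. This rests on the schedule being what the site follows and on the two rows having been read correctly; their identical pattern supports the reading.

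The primary endpoint, the diary endpoints at every time including 1 month, and the questionnaire comparisons at 3 and 6 months stand. The point should be fixed, but it does not threaten the trial's main conclusion.

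**What to change.** The sponsor should choose one of two reconciliations:

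1. **Collect the data.** Mark SNOT-22 and MFIQ at Visit 3 (Day 30) in Section 1.3. The burden is 22 + 26 = 48 self-administered items, once, at a visit subjects already attend. If enrolment is under way, only subjects who have yet to reach Visit 3 will have a 1-month score. The plan should then say so and state how that reduced set will be reported.
2. **Drop the time point.** If Visit 3 collection is no longer possible or not wanted, delete the 1-month comparison for these two instruments in Sections 1.1, 1.4, 8.1 and 8.4.3. The lead-in sentence in the synopsis also governs the diary outcomes, so the two questionnaires need their own line. Deleting 1 month from the shared sentence would remove valid diary comparisons.

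Two wording corrections belong in the same amendment. In the synopsis, the late time point for the two questionnaires should read 6 months, matching the other sections and the single Day 180 form. Section 8.1 should say whether an MFIQ total is analysed besides the five domains.

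Under the Statement of Compliance, either route needs IRB approval and submission to the FDA before implementation. Neither touches treatment, sample size or the primary analysis.
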